6.0 Procedures

Clinical Assessments	Day -28	monthly	EOT 13	Week 12 post	
	to Day 1	3 days \pm	-3 days up to + 4 weeks	-3 days up to + 4 weeks	
Informed Consent	X				
Audit -questionnaire	X	X	X	X	
WPAI, SF-36	X	X	X	X	
History & Physical	X		X	X	
Height, Weight	X		X	X	
Vital Signs	X		X	X	
Adverse Events	X	X	X	X	
CBC& WBC differential	X		X	X	
PT, INR	X				
Complete metabolic panel	X	X	X	X	
FIBRO Spect II Index PRN	X				
HCV RNA (within 6 months)	X		X	X	
Ultrasound abdomen (within 6 months)	X				
Fibroscan PRN	X				
Serum Pregnancy test PRN	X				
Urine Drug Screen	X				
Hepatis B surface antigen	X				
HIV panel	X				
Urinalysis	X				
Hemoglobin A1C	X				
Nursing/ Coordinator Visit		X	X	X	
Harvoni reconciliation (pill count)		X	X		
Medication \pm alcohol consumption diary	X	X	X	X	

Protocol Version 3.0 01-Sep-2017, 2.0, 05-June 2017, version 1.0, 01-jan-2016,

6.2 Monthly Nursing/ Coordinator visits

Subjects will have a monthly visit with the nursing coordinator of the study \pm 3 days. This will be to assess drug adherence and accountability as well as to monitor for side effects and obtain alcohol consumption information we will also administer QOL questionnaires (WPAI, SF-36, Audit)

6.3 Post Treatment Assessments

All subjects must complete the Post-Treatment EOT, and 12 week visit. For subjects who have completed an EOT, the post treatment 12 visit will be scheduled 12, after the last dose of therapy dose -3 days up to 4 weeks.

6.4 Removal from Protocol Therapy

- Extraordinary medical circumstances: if at any time the constraints of this protocol are detrimental to the subject's health (unacceptable toxicity), the subject will be removed from protocol therapy.
- Subject chooses to discontinue treatment.

7.0 Adverse Events Management

7.1 Adverse Events

An adverse event (AE) is any untoward medical occurrence in a patient or clinical investigation subject administered a pharmaceutical product and which does not necessarily have a causal relationship with this treatment. An adverse event (AE) can therefore be any unfavorable and unintended sign (including an abnormal laboratory finding), symptom, or disease temporally associated with the use of a medicinal (investigational) product, whether or not related to the medicinal (investigational) product. (¹¹ICH GCP)

7.2 Assessment of Adverse Events

AEs will be collected from the time the subject signed the consent form and ending at the 24week follow up appointment. Severity of the AE will be reported in the AE case report form (CRF) and will be determined by the principal investigator according to the NCI common toxicity Criteria 4.0. The AE entry will indicate whether the AE was serious, onset, resolution, and whether or not the AE was related to the investigational medicinal product and if the actions taken as well as the severity.

The NCI Common Toxicity Criteria Adverse Events version 4.0 will be used to grade AE's.

Protocol Version 3.0 01-Sep-2017, 2.0, 05-June 2017, version 1.0, 01-jan-2016,

7.3 Serious Adverse Events

Any adverse drug experience occurring at any dose that results in any of the following outcomes:

- Death
- Life-threatening situation (subject is at immediate risk of death)
- In-patient hospitalization or prolongation of existing hospitalization (excluding those for study therapy or placement of an indwelling catheter, unless associated with other SAEs)
- Persistent or significant disability/incapacity
- Congenital anomaly/birth defect in the offspring of a subject who received investigational medicinal product
- Other: medically significant events that may not be immediately life-threatening or result in death or hospitalization, but based upon appropriate medical and scientific judgment, may jeopardize the subject or may require medical or surgical intervention to prevent one of the outcomes listed above

7.4 Serious Adverse Event Reporting

- UNMC's IRB
- Unexpected serious adverse drug reaction
- Any death which occurs while the subject is being treated on protocol or occurs within 30 days of completing research related interventions
- The contact information is: Institutional Review Board, UNMC [name]; [contact]; email [contact]
- The investigator will utilize the FDA MedWatch form for the reporting of adverse events to Gilead and follow up information to those events. The form can be found at the following URL: <http://www.fda.gov/medwatch>
- Data Safety Evaluations of adverse events will be monitored via submission to The Non-cancer UNMC DSMB. All adverse events (possibly, probably or definitely) grade 3 or higher will be submitted to the above independent physicians to review for trial safety and statistical considerations every three months.

7.5 Study Stopping Rules

If any of the three criteria below are met, the trial must be paused and evaluated for safety by the DSMB. The trial may continue after the DSMB determines causality is not associated with the study drug.

Protocol Version 3.0 01-Sep-2017, 2.0, 05-June 2017, version 1.0, 01-Jan-2016,

- ≥ 3 grade 3 NCI CTCAE version 4.0 in the same category
- ≥ 2 grade 4 NCI CTCAE version 4.0 in the same category
- ≥ 1 grade 5 NCI CTCAE version 4.0 in the same category

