3.2 Dose Modifications

There will be no dose modifications. If the subject has toxicities that are not tolerable it is advised to stop the therapy and the subject will be removed from the protocol.

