8.2 Sample size justification

30 patients will be accrued to the study with the goal of estimating the true proportion of patients continuing to ingest alcohol who achieve complete eradication at 12 weeks.

It is anticipated that approximately 92% of patients will achieve eradication at 12 weeks based on previous research of 400 patients who received the study drug. A sample size of 30 produces a two-sided 95% confidence interval with a width equal to 0.23 when the sample proportion is 0.92.

We assume a screen failure or with drawl rate of 15%. We will need to consent 36 patients.

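### The pause triggers in section 7.5 name exact grades, so two grade 3 events plus one grade 4 event in a category do not pause the trial, although three grade 3 events do

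*Combined protocol and SAP*

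**What the plan says.** Section 7.5 (Study Stopping Rules) lists three criteria and makes any one of them sufficient: "If any of the three criteria below are met, the trial must be paused and evaluated for safety by the DSMB". The first criterion concerns severe events and reads "≥ 3 grade 3 NCI CTCAE version 4.0 in the same category". The second has the same form with a lower count for the next grade up, "≥ 2 grade 4 NCI CTCAE version 4.0 in the same category". The third lowers the count once more, so that a single fatal (grade 5) event is enough.

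In each line the inequality sign applies to the number of events, not to the grade. The section has no relatedness filter: the DSMB settles causality after the pause and decides then whether the trial may go on.

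Two other provisions bear on the point. Section 7.4 has a routine three-monthly DSMB submission, in different words: "All adverse events (possibly, probably or definitely) grade 3 or higher will be submitted". Section 3.2 deals with the individual patient who has intolerable toxicity: "it is advised to stop the therapy and the subject will be removed from the protocol".

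**The concern.** The thresholds fall from 3 to 2 to 1 as the grade rises, so the rule is evidently meant to react sooner to more severe events. Read as written, it does the opposite in one situation. Suppose a category already holds two grade 3 events. If the third event is grade 3, the trial pauses. If it is grade 4, the trial carries on.

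What is at stake is the mandatory pause and the prompt evaluation that goes with it. In this mix they come one event late, or do not come at all if no further event of grade 3 to 5 occurs in that category. Safety and tolerability is one of the two primary objectives (section 2.1), and the patients are drinking at a harmful or hazardous level and may have cirrhosis (section 4.1).

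**Working it through.** **Inputs.** The three triggers and their either/or combination come from section 7.5. The number of patients, 30, comes from section 8.2. The protocol states no pause probability, so there is no figure of its own to reproduce. It also gives no toxicity rates, so the rates below are assumptions.

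**Step 1: where the two readings differ.** Let a, b and c be the numbers of grade 3, 4 and 5 events in one category.

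- As written: pause if a ≥ 3, or b ≥ 2, or c ≥ 1.
- Cumulative (*grade 3 or higher*, *grade 4 or higher*): pause if a+b+c ≥ 3, or b+c ≥ 2, or c ≥ 1.

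Any c ≥ 1 or b ≥ 2 pauses under both readings. With c = 0 and b = 0, both need a ≥ 3. With c = 0 and b = 1, the written rule needs a ≥ 3 and the cumulative rule needs a ≥ 2. They therefore differ only at (a, b, c) = (2, 1, 0). Enumerating all counts from 0 to 7 per grade gives the same single state, and no state where the written rule pauses and the cumulative one does not.

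**Step 2: how long the gap lasts.** One more event from (2, 1, 0) gives (3, 1, 0), (2, 2, 0) or (2, 1, 1). Each meets a trigger as written, so the gap ends at the next grade 3, 4 or 5 event in that category.

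**Step 3: how often it would occur.** Assume one category, each of 30 patients counted once at worst grade, independent patients and no grade 5 events. Write p3 and p4 for the per-patient rates, and q = 1 − p3 − p4.

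- P(a, b) = 30! / (a! b! (30−a−b)!) × p3^a × p4^b × q^(30−a−b)
- Pause as written = 1 − sum of P(a, b) over a = 0, 1, 2 and b = 0, 1
- Pause missed altogether = P(2, 1), since the trial ends in the gap state
- Pause with cumulative wording = pause as written + P(2, 1)
- Ever in the gap state = P(at least 3 events) × 3 × (p3/s)² × (p4/s), with s = p3 + p4. The first three events must be two of grade 3 and one of grade 4, in any order.
- Pause one event late = ever in the gap state − P(2, 1)

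Worked example at p3 = 2%, p4 = 1%:

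- Multinomial coefficient: 30 × 29 × 28 / 2 = 12,180.
- Missed: 12,180 × 0.02² × 0.01 × 0.97^27 = 0.04872 × 0.4394 = 0.0214.
- Pause as written: 1 − (0.4010 + 0.1240 + 0.2480 + 0.0742 + 0.0742 + 0.0214) = 0.0572.
- Cumulative: 0.0572 + 0.0214 = 0.0786.
- Ever in the gap: 0.0601 × 3 × (2/3)² × (1/3) = 0.0601 × 0.4444 = 0.0267.
- Late: 0.0267 − 0.0214 = 0.0053.

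| Assumed grade 3 / grade 4 rate | Pause, as written | Pause, cumulative | Missed (points) | One event late (points) |
|---|---|---|---|---|
| 1% / 0.5% | 1.3% | 1.7% | 0.4 | 0.05 |
| 2% / 1% | 5.7% | 7.9% | 2.1 | 0.5 |
| 5% / 2% | 28.8% | 37.4% | 8.6 | 6.8 |
| 10% / 3% | 69.0% | 77.5% | 8.5 | 22.9 |

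The late pauses are part of the as-written column; the missed ones are not.

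**The case against.** The strongest reply is that the three lines are shorthand (they even leave out the word *event*) and that a sensible DSMB would count a grade 4 event toward the grade 3 tally. That reading is plausible and may be what was intended. It is not written, however, and section 7.4 shows that the authors spelled out *or higher* when they wanted it. A mandatory pause should not depend on the reader supplying those words.

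The second reply is that the DSMB sees these events anyway through section 7.4. This stands in part: a related cluster of two grade 3 events and one grade 4 event does reach the DSMB, so what can be lost is the pause and its event-driven evaluation, not all DSMB review. But the submission is three-monthly, treatment lasts 8 or 12 weeks (section 3.1), and a course could finish between submissions. The submission also leaves out events judged unrelated, which section 7.5 counts. That last gap is narrow, since the DSMB would release a truly unrelated cluster, but it leaves the investigator's attribution unchecked. Sections 3.2 and 6.4 protect individual patients and do not pause the trial.

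The third reply is that the rates are assumed and the two upper rows may be too high. At 10%/3%, 30 patients would yield an expected 30 × 0.10 = 3 grade 3 and 30 × 0.03 = 0.9 grade 4 patients in one category, for a drug that section 1.1 describes as well tolerated. This stands: the lower rows may be the more realistic ones, and there the gap is small. Counting patients at worst grade is also a choice, because section 7.5 does not say whether it counts events or patients. The existence of the gap needs none of these assumptions.

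**Conclusion.** The concern holds and is minor. On the wording of section 7.5, one more severe cluster escapes a pause that a milder cluster triggers. That conclusion rests on the text alone. The defect is confined to one count pattern per category and lasts until the next grade 3 to 5 event there.

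Its frequency depends on assumed rates. The pause is missed in 0.4 to 2.1 percentage points of trials at the two lower pairs of rates and in about 8.5 points at the two higher pairs, with late pauses in addition. SVR12, its confidence interval and the primary safety endpoint do not change.

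**What to change.** In section 7.5, reword the first trigger to three or more events of *grade 3 or higher* in the same category, and the second to two or more events of *grade 4 or higher* in the same category. Leave the grade 5 trigger and the thresholds of 3, 2 and 1 as they are. This brings the section into line with the phrasing already used in section 7.4. The sponsor and the DSMB should confirm the wording.

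The cost is two phrases in a protocol amendment. The only operational downside is a pause one event earlier in the mixed cluster described here. Sample size, endpoints and analysis stay the same.

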8.0 Statistical Considerations

8.1 Criteria for Response

Response Assessment: will be the HCV RNA obtained at EOT, weeks 12. The subject's HCV RNA level should be less than LLOQ for eradication.

8.2 Sample size justification

30 patients will be accrued to the study with the goal of estimating the true proportion of patients continuing to ingest alcohol who achieve complete eradication at 12 weeks.

It is anticipated that approximately 92% of patients will achieve eradication at 12 weeks based on previous research of 400 patients who received the study drug. A sample size of 30 produces a two-sided 95% confidence interval with a width equal to 0.23 when the sample proportion is 0.92.

We assume a screen failure or with drawl rate of 15%. We will need to consent 36 patients.

8.3 Statistical analysis

Descriptive statistics (means, standard deviations, medians, interquartile ranges, frequencies, and percentages) will be used to summarize demographic characteristics and clinical measurements of the study population. The incidence of complete eradication at 12 weeks will be estimated with a proportion and

Protocol Version 3.0 01-Sep-2017, 2.0, 05-June 2017, version 1.0, 01-jan-2016,

associated 95% confidence interval. Counts and percentages will be used to summarize medication side effects. Compliance, as measured by pill counts over the study period, will be evaluated using descriptive statistics (mean, standard deviation, median, and interquartile range).

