2.0 Objectives and Endpoints

2.1 Primary Objectives:

- To determine the antiviral efficacy of LDV/SOF (SVR12) in alcoholics.
- To evaluate the safety and tolerability of LDV/SOF as assessed by review of the accumulated safety data.

2.2 Secondary Objectives:

- To assess HCV RNA at EOT, 12 weeks after therapy
- To assess the adherence of the LDV/SOF in subjects using a monthly calendar and monthly nursing assessment
- To assess changes in the QOL of the subjects from baseline to end of study with the CLDQ-HCV, SF-36 questionnaire and WPAI scores.

2.3 Primary Endpoints:

- The primary efficacy endpoint is SVR12 (HCV RNA <LLOQ 12 weeks after discontinuation of study drug).
- The primary safety endpoint is any AE leading to permanent discontinuation of study drug.

2.4 Secondary Endpoints:

- The proportion of subjects with HCV RNA < LLOQ at EOT

Protocol Version 3.0 01-Sep-2017, 2.0, 05-June 2017, version 1.0, 01-jan-2016,

- The adherence rates by pill count and attendance at monthly nurse visits changes in QOL scores (CLDQ-HCV, SF-36, WPAI) from baseline to end of study
- The proportion of patients who are able to complete therapy.

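### Does section 8.3 leave the primary safety endpoint without an analysis by summarising only medication side effects?

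*Combined protocol and SAP*

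**What the plan says.** Section 2.3 names two primary endpoints, SVR12 and a safety endpoint: "The primary safety endpoint is any AE leading to permanent discontinuation of study drug". Section 7.1 defines an AE as an untoward event "whether or not related to the medicinal (investigational) product".

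Section 8.3 treats the two differently. For efficacy, "The incidence of complete eradication at 12 weeks will be estimated with a proportion and" a 95% confidence interval. For safety, the whole text is "Counts and percentages will be used to summarize medication side effects". Discontinuation is not mentioned in 8.3, and sections 8.1 and 8.2 deal only with HCV RNA response.

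Other sections bear on the point:

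- Section 2.1 says safety and tolerability will be judged by reviewing the safety data as they accumulate.
- Section 6.2 has the monthly nurse visit assess adherence "as well as to monitor for side effects", without defining that term.
- Section 7.2 requires each AE entry to record "whether or not the AE was related to the investigational medicinal product and if the actions taken", along with seriousness, severity, onset and resolution.
- Section 2.4 lists as a secondary endpoint: "The proportion of patients who are able to complete therapy".
- Section 6.4 gives two routes off therapy: unacceptable toxicity, and "Subject chooses to discontinue treatment".

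**The concern.** A primary endpoint should be traceable from its definition to its analysis, and here the link is not written down. The phrase used in 8.3 is undefined and does not match the endpoint. It is wider in one respect, because it takes in events that do not stop treatment. It may be narrower in another, because side effects of a medication can be read as events attributed to the drug.

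The second reading is the one that could matter. The subjects are expected to keep drinking, section 1.1 says alcohol abuse may itself raise liver enzymes, and there is no control arm. Whether a stop was caused by drug or alcohol is then a judgement. A drug-attributed count could make the regimen look better tolerated than an all-cause count would.

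The lack of an interval adds to this, since a bare 0% in a small trial can be mistaken for evidence that the event is rare. The completion endpoint in 2.4 is no substitute, because it mixes stops for toxicity with stops by choice.

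**Working it through.** **1. Which events count.** Section 2.3 says any AE leading to permanent discontinuation. Section 7.1 says AEs include unrelated events. Together they give one event set: all-cause AEs that end treatment. Section 8.3 does not redefine the endpoint; it describes how safety events in general will be tabulated. A drug-attributed count presented as the primary safety result would contradict 2.3, so it is not a second reading that the plan permits.

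**2. Whether the data exist.** Section 7.2 records relatedness and action taken for each AE. Section 6.4 separates toxicity from choice as a reason for stopping. The endpoint can be derived from what is collected.

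**3. The plan's own precision figure.** Section 8.2 gives a two-sided 95% interval of width 0.23 at n = 30 and a sample proportion of 0.92. The exact (Clopper-Pearson) method with x = 30 × 0.92 = 27.6 gives limits 0.761 and 0.987, so the width is 0.226, which rounds to 0.23. The figure reproduces. It concerns eradication only; no precision is claimed for safety.

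**4. What an interval would add for safety.** The documents give no expected discontinuation rate, so the event counts here are assumptions, with 30 subjects dosed. For zero events the exact upper limit is 1 − 0.025^(1/n). At n = 30 this is 1 − 0.025^(1/30) = 0.1157. For one or more events the limits are beta quantiles.

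| Events of 30 | Rate | Exact 95% interval |
|---|---|---|
| 0 | 0% | 0 to 11.6% |
| 1 | 3.3% | 0.1 to 17.2% |
| 2 | 6.7% | 0.8 to 22.1% |
| 3 | 10.0% | 2.1 to 26.5% |

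Each interval is a function of the count and the denominator alone. Once these are reported, any reader can obtain it.

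**5. Sensitivity to the denominator.** Section 8.2 reaches 36 consented subjects from 30/(1 − 0.15) = 35.3, rounded up, and its 15% pools screen failures with withdrawals. If some withdrawals come after dosing, the number treated could lie between 30 and 36. With 0 of 36, the upper limit is 1 − 0.025^(1/36) = 0.097, or 9.7%. The message is the same.

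**6. Size of the attribution effect.** With k all-cause stops and j judged drug-related, the reported rates differ by (k − j)/30. For k = j the difference is 0. For k = 1, j = 0 it is 1/30 = 3.3 points. For k = 3, j = 0 it is 3/30 = 10.0 points, and the upper limit moves from 26.5% to 11.6%, about 15 points. Both k and j are assumed, and nothing in the documents makes the extreme case more likely than no difference.

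**The case for a change.** The best case for a change is that section 8 is the only statistical plan and one of two primary endpoints does not appear in it. A sentence naming the event, the denominator and an exact interval would cost almost nothing, need no new data, and give safety the treatment that 8.3 already gives SVR12. In a single-arm trial in drinkers, attribution is where a safety result can drift.

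Part of this stands. The cross-reference is missing, the term in 8.3 is loose, and an analyst who prints the exact interval beside the count does the reader a service. What does not stand is the step from loose wording to a wrong result. That step needs the analyst to set aside the definition in 2.3, to adopt one reading of an undefined phrase, and to have several stops judged unrelated. The trial is also a descriptive pilot, with its size justified only for estimating eradication, so the absence of a safety interval contradicts nothing in the plan.

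One could also point to the data safety monitoring board (DSMB) listing in 7.4, which seems to carry an attribution filter that the pause criteria in 7.5 lack. That rests on supplying a word missing from 7.4. A quarterly listing and a pause trigger serve different purposes and need not count the same events, so no contradiction is shown. Neither passage governs the analysis of the endpoint.

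**Conclusion.** The omission is real but inconsequential: it is a gap that a competent analyst fills in the only way 2.3 and 7.1 allow, by reporting how many treated subjects permanently stopped study drug because of any AE, related or not, with the percentage. The interval is a presentational extra; with no events it would run from 0 to 11.6% if 30 are dosed, or to 9.7% if 36 are. The possible shift of 0 to 10 points from an attribution filter depends on assumed counts of 1 to 3 events and on a count that would not be the stated endpoint. The conclusion assumes that the action-taken entry in 7.2 identifies permanent discontinuation, which is its ordinary use; the case report form is not among the documents. No change to the plan is needed.

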9.0 Publication Plan

Conference/Year: DDW or AASLD 2017

Publication/Year: Hepatology 2017 or 2018

